A high-contrast, black and white image showing a large, dark, irregular shape against a white background. The dark shape has several jagged, stepped edges, resembling a 3D block or a heavily processed photograph of a physical object. The overall appearance is abstract and geometric.

For more information, contact the Office of the Vice President for Research and Economic Development at [contact] or [contact].

10 of 10

11. **What is the primary purpose of the *Journal of Clinical Endocrinology and Metabolism*?**

4.3.1.2 Magnetic Resonance Spectroscopy Scans

The change in hepatic glycogen concentration will be measured using an MRS scanner with C-13 imaging capability; serial scans will be performed on Day -1, Day 1 prior to investigational product administration and on Days 28 and 29 (Part A) and Days 35 and 36 (Part B) at the time points specified in the schedules of procedures. MRS/MRI will also be used to evaluate liver volume and hepatic fat fraction (the latter in Part B of the study only). Investigators should refer to the study manual provided for further information detailing the procedure for performing MRS and MRI scans.

4.3.2 Safety Assessments

4.3.2.1 Medical History and Physical Examination

Complete medical history will include history (including smoking and alcohol history) and current medical conditions, past or present cardiovascular disorders, respiratory, GI, renal,

hepatic, neurological, endocrine, lymphatic, haematologic, immunologic, dermatological, psychiatric, genitourinary, drug and surgical history, or any other diseases or disorders.

Physical examinations will be performed by a physician or qualified designee and will include examination of the following body systems: immunologic/allergy; head, ears, eyes, nose, and throat; respiratory; cardiovascular; GI; musculoskeletal; neurological (structured neurological examination to encompass mental status, cranial nerves, nystagmus; motor system-muscle strength, sensory system-sensation, bowel and bladder function, deep tendon reflexes, gait, station, coordination, fundoscopy, and cerebellar function); psychiatric (to the extent of determining whether or not the subject is willing and able to cooperate with the required study procedures in the investigator's judgment); dermatological; haematologic/lymphatic; and, endocrine.

Any focal deficit identified at baseline should be documented in the eCRF.

The full physical examination including a structured neurological examination is required at screening ([Table 6](#)). Abbreviated physical examinations (evaluation of selective body systems at the judgment of the physician or qualified designee based on subject presentation) are sufficient for the remaining time points (ie, randomised treatment and follow-up periods) ([Table 7](#), [Table 8](#), [Table 9](#), [Table 10](#), and [Table 11](#)).

Clinically significant abnormal findings will be recorded.

4.3.2.2 Assessment of the Injection Site

Study centre staff will check the injection site for injection site reactions during study visits as required. Injection site reactions may include (but are not limited to) local erythema, pain, tenderness, induration, swelling, pruritus, ulceration, and pigmentation.

4.3.2.3 Electrocardiograms

At the visits specified in the schedules of procedures, ECGs will be obtained after 10 minutes supine rest. Only a single digital ECG recording will be required at the specified time points.

The same recorder will be used for each subject at each time point, if possible. Date and time settings should be checked at the start of each study day and aligned with an official timekeeper for all machines used in the study.

Skin preparation should be thorough and electrode positions should be according to standard 12-lead ECG placement.

In this study lead V2 or II will be analysed and reported as primary. Lead V5 will be analysed, for all visits, as backup for the individual where analysis in lead V2 or II is not deemed possible for predose or significant parts of whole visits or whole visits.

The following variables will be reported: heart rate, RR, PR, QRS, and QT intervals from the primary lead of the digital 12-lead ECG. The investigator may add extra 12-lead ECG safety assessments if there are any abnormal findings or if the investigator considers it is required for any other safety reason.

4.3.2.4 Vital Signs

Vital sign measurements (BP, heart rate, body temperature, and respiration rate) will be obtained after the subject has rested in either a seated or supine position for at least 10 minutes at the time points specified in the schedules of procedures (for time points where ECG recording precedes vital sign measurement, the 10-minute rest in the supine position prior to the ECG suffices for the rest prior to vital sign measurement). Blood pressure should be measured once at heart level in the non-dominant arm where possible, with the subject seated or supine and rested for 10 minutes prior to the measurement. Route of body temperature measurement will be according to local protocols.

4.3.2.5 Weight, Height, and Body Mass Index Calculation

Weight (kg), height (cm), and BMI (kg/m²) will be measured at screening. Weight will be measured at all other time points specified in the schedules of study procedures.

4.3.3 Clinical Laboratory Tests

A Laboratory Manual will be provided to the sites that specifies the procedures for collection, processing, storage, and shipment of samples, as well as laboratory contact information, specific to this clinical research study.

Clinical laboratory safety tests including serum pregnancy tests will be performed in a licensed central or licensed local clinical laboratory. Urine pregnancy tests may be performed at the site using a licensed test (dipstick). Abnormal laboratory results should be repeated as soon as possible (preferably within 24 to 48 hours).

The following clinical laboratory tests will be performed (refer to time points in the schedules of procedures):

Haematology Panel

White blood cell count with differential	Platelet count
Red blood cell count	Mean corpuscular volume
Haematocrit	Mean corpuscular haemoglobin concentration
Haemoglobin	

Serum Chemistry Panel

Calcium	ALP
Potassium	Total bilirubin

Sodium	Creatinine
Bicarbonate*	Blood urea
AST	Albumin
ALT	Magnesium

ALP = alkaline phosphatase; ALT = alanine transaminase; AST = aspartate transaminase.

Notes:

Liver function tests = AST, ALT, ALP, total bilirubin, and albumin

Tests for AST, ALT, ALP, and total bilirubin must be conducted concurrently and assessed concurrently.

* may be measured via serum chemistry sample of blood gas analyser per local procedures.

Urinalysis

Protein	Urine drug screen*
Glucose	Ketones
Blood	

Note: Urinalysis for protein, glucose, ketones, and blood may be performed at the site using a licensed test (dipstick).

*Illicit drug panel will test for the following drugs; amphetamines, barbituates, benzodiazepines, cocaine, opiates (morphine, heroin), methamphetamine, cannabinoids (marijuana), methadone, phencyclidene, methylenedioxymethamphetamine (ecstasy), propoxyphene, tricyclic antidepressants. Subjects who use tricyclic antidepressants or benzodiazepines for an established clinical indication may be permitted to enter the study based upon the judgement of the investigator.

Other Laboratory Tests

- Calcitonin
- Alcohol screening test (breath or urine based test)
- Pancreatic amylase, lipase
- HbA1c
- Anti-drug antibodies (immunogenicity)
- Serum or urine pregnancy test (for females with childbearing potential only)
- HBsAg, hepatitis C antibody (screening only)
- HIV-1, -2 antibodies (screening only)
- Glucose metabolism panel for MMTT: Timed glucose
- Fasting lipid profile: high-density lipoprotein, low-density lipoprotein, triglycerides
- Gluconeogenic substrates: free fatty acids, beta-hydroxybutyrate, acetoacetate, amino acids, and lactate
- Glucose samples to measure ²H labelled glucose

4.3.3.1 Glucose Meter Measured Capillary Plasma Glucose Readings

At the start of the study, each subject will be issued a standardised glucose meter, testing strips, and a diary. Subjects will be encouraged to perform finger-prick tests if they feel unwell and in particular if they feel the symptoms may be due to hypoglycaemia for the duration of the study, but they will not be required to test routinely. If the investigator/site staff feel that a subject could be experiencing hypo- or hyperglycaemia, capillary plasma glucose should be tested with a standardised glucose meter. Capillary plasma glucose levels of < 3 mmol/L (54 mg/dL) should be recorded as an AE regardless of whether the subject has symptoms or not.

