1.5 Rationale for Conducting the Study

MEDI0382, a GLP-1 receptor and glucagon receptor co-agonist is under development for the treatment of T2DM and NASH. Clinical studies to date have shown significant reductions in blood glucose levels in treated subjects, despite the known action of glucagon receptor agonists to increase blood glucose levels. The study of glucose and glycogen metabolism is therefore important to gain an increased understanding of the mechanism of action of MEDI0382.

Glucagon primarily raises blood glucose levels via increased hepatic glucose output. This is initially achieved via an increase in glycogenolysis, and later enhanced gluconeogenesis (Cherrington et al, 1981). In contrast, GLP-1 promotes glucose-dependent insulin release which both suppresses gluconeogenesis and promotes glycogen synthesis and hepatic glucose uptake. However, the relative contribution of each of these counter-regulatory mechanisms to hepatic glucose and glycogen metabolism in the setting of dual glucagon and GLP-1 receptor agonism is at present unclear. Furthermore, an added level of complexity is that subjects with T2DM exhibit dysregulated hepatic glucose production in the fasted state, with an imbalance towards heightened gluconeogenesis over glycogenolysis in contrast to healthy subjects (Savage et al, 2007). Finally, as hepatic expression of the glucagon receptor is far greater than that of the GLP-1 receptor, results obtained in this study may provide evidence of target engagement of MEDI0382 with the glucagon receptor, and could serve to differentiate MEDI0382 from GLP-1 receptor mono-agonists (Uhlén et al, 2015).

[figure not shown]

Table 1 Fasting Glucose and Liver Glycogen Content at Termination (Day 14) in DIO Mice, Group Means \pm SEM

DIO = diet-induced obesity; eqv = equivalent; SEM = standard error of the mean

*p < 0.05; **p < 0.01; ***p < 0.001; ****p < 0.0001

N = 6 female mice/group

Source: Study AZM110628-01-18

In prior clinical studies in overweight and obese subjects with T2DM dosed with MEDI0382 for 41 days, marked reductions in both fasting and postprandial blood glucose levels were observed; however, measures of hepatic glycogen content were not performed.

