1.6 Benefit-Risk and Ethical Assessment

The study will be performed in accordance with ethical principles that have their origin in the Declaration of Helsinki and are consistent with International Council on Harmonisation (ICH)/Good Clinical Practice, and applicable regulatory requirements.

MEDI0382 is a GLP-1 receptor and glucagon receptor co-agonist that promotes glucose lowering and weight loss and is targeted at subjects with T2DM. MEDI0382 has the potential to deliver improvements in glycaemic control and lipid homeostasis, and is anticipated to be a useful therapy for T2DM. However, it should be noted that given the short treatment duration in this study little direct benefit to the patient's underlying T2DM should be expected.

Nausea and vomiting events have been observed in other clinical studies with MEDI0382. The study protocol includes strategies to manage gastrointestinal AEs if they arise, including reduction of meal sizes and maintaining adequate hydration. As clinical data for MEDI0382 is still limited, potential risks for MEDI0382 are based on published data for GLP-1 receptor agonists and glucagon receptor co-agonists in addition to available nonclinical data and clinical data for MEDI0382. According to the latest version of the IB, potential risks for MEDI0382 include an increase in heart rate, alterations in blood pressure, QT interval prolongation, anaphylactic-type reactions, injection site reactions, skin rash, pancreatitis, pancreatic carcinoma, and thyroid cancer.

The study design aims to minimise potential risks to subjects participating in this study based on the proposed inclusion/exclusion criteria, safety monitoring, and up-titration dosing schedule. All subjects will be monitored throughout the study to ensure adequate glycaemic control. Subjects will be given appropriate training in SC injection administration as well as use of any devices. Subjects with contraindications to magnetic resonance imaging (MRI) scanning are excluded from the study.

Refer to Section 1.4 and the current IB for further information on the potential benefits of MEDI0382 and an assessment of the potential and known risks.

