3.1.4.3 Hyperglycaemia

In the event of suspected persistent hyperglycaemia in a subject based on either symptoms of hyperglycaemia (eg, thirst, polyuria, blurred vision) or capillary plasma glucose readings (eg, 3 readings > 260 mg/dL [14.4 mmol/L] within one week), the investigator should perform additional fasting blood glucose levels as necessary. If 2 or more laboratory plasma fasting

glucose levels of > 260 mg/dL [14.4 mmol/L] more than 3 days apart are detected, the investigator should consider rescue therapy following discussion with the medical monitor.

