^k Following a minimum 14 hr fast, a MMTT will be performed at 0800 ± 15 min on Day -1; baseline blood samples will be collected at T = 0 (alongside samples for other blood tests and 2H labelled glucose); a standardised liquid meal will be given to subjects and consumed in entirety within 5 min. Further blood samples for glucose levels will be collected at T = 15, 30, 45, 60, 120, 180 and 220 min (± 5 min). Note that the start time of the MMTT may be adjusted to 1 hr before or 1 hr after provided all other related procedures are performed at the same time intervals.

^l MRS scans will be performed on Day -1 at 0700, 1300, 2200 (± 15 min) and on Day 1 at 0800 (24 hours post MMTT) (± 15 min). Note that times may be adjusted to 1 hr before or 1 hr after provided all other related procedures are performed at the same time intervals. The MRS scan that will be used to evaluate liver fat content should be performed whilst the subject is fasted and may occur on Day -1 or Day 1.

^m AEs will be assessed from the start of investigational product administration; SAEs will be assessed from the time of signed informed consent form.

ⁿ Injection training should be performed with Placebo MEDI0382 pens prior to Day 1 and with the randomised investigational product on Day 1; subjects should be provided with as much training as they need to be comfortable with self-injection using the pen device between Day -3 through Day 1.

^o On Day -1 or Day 1, subjects will be randomised to receive investigational product: MEDI0382 or placebo or liraglutide. Subjects enrolled in Part A will not be re-enrolled in Part B.

^p A glucose meter, test strips, and a diary should be provided to the subject. The subject should be trained in its use and advised to test their capillary blood glucose at any time the subject feels unwell or has symptoms of hypoglycaemia (hunger, dizziness, shaking, sweating, or irritability) and they should record these symptoms and a capillary plasma glucose level in their diary only when symptomatic. Subjects should do this until their final study visit and bring the diary card with them to their next visit if they recorded symptoms or capillary plasma glucose levels while at home.

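### Section 1.6 says glycaemic control is monitored throughout, but Part B schedules no plasma or capillary glucose between the first dose and Day 35

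*Protocol*

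**What the plan says.** **The commitment.** Protocol Section 1.6 lists the measures that limit risk to subjects and states: "All subjects will be monitored throughout the study to ensure adequate glycaemic control".

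**The rule.** Section 3.1.4.3 deals with suspected persistent hyperglycaemia. It opens on symptoms (its examples are thirst, polyuria and blurred vision) or on "capillary plasma glucose readings (eg, 3 readings > 260 mg/dL [14.4 mmol/L] within one week"). The investigator then obtains further fasting glucose as needed. Rescue is to be considered if two or more laboratory fasting "glucose levels of > 260 mg/dL [14.4 mmol/L] more than 3 days apart are detected".

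**Meter testing.** Section 4.3.3.1 gives each subject a meter, strips and a diary. It encourages a finger-prick test when the subject feels unwell, above all if hypoglycaemia is suspected, "for the duration of the study, but they will not be required to test routinely". It adds: "If the investigator/site staff feel that a subject could be experiencing hypo- or hyperglycaemia, capillary plasma glucose should be tested". Table 9 footnote p (Section 4.2.2, Part B) tells subjects to test if they feel unwell or have hypoglycaemia symptoms, and says "they should record these symptoms and a capillary plasma glucose level in their diary only when symptomatic".

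**Laboratory testing.** Under "Serum Chemistry Panel", Section 4.3.3 lists twelve analytes: calcium, potassium, sodium, bicarbonate, AST, ALT, ALP, total bilirubin, creatinine, urea, albumin and magnesium. Glucose is not among them. The only laboratory glucose concentration in that section is the timed glucose of the mixed-meal tolerance test (MMTT). Urinalysis includes a glucose dipstick.

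**The concern.** Section 1.6 offers glycaemic monitoring as a safeguard, so one expects the schedule to deliver it. Between the first dose and Day 35 of Part B the schedule relies wholly on someone noticing a problem. One of the two ways into the Section 3.1.4.3 rule is a run of capillary readings, yet none is scheduled and subjects need not test routinely. The prompt they are given is also built around hypoglycaemia.

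At stake is the safety of subjects with type 2 diabetes, including a placebo arm, whose metformin is interrupted twice. Interpretation is affected too: safety is a secondary objective, and a low count of hyperglycaemia events says less when glucose was not routinely looked for.

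**Working it through.** This is an audit of the schedule; no sample size, power or error rate is in dispute.

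**Step 1. Glucose information scheduled in Part B** (Tables 9 to 11, Section 4.3.3)

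| Day | Status | Plasma or capillary glucose concentration | Other |
|---|---|---|---|
| -1 | before treatment | timed MMTT glucose | |
| 1 | before first dose | none | chemistry; urine dipstick as the table reads |
| 8 | seven doses taken | none | chemistry after a fast of at least 8 hours |
| 14/15, 21/22 | home dosing | none | remote contact: titration, adverse events, concomitant medication |
| 33, 34 | inpatient | none | Day 34 deuterium-glucose sample |
| 35 | last dose | timed MMTT glucose | |
| 36 | after last dose | none | chemistry, HbA1c, urine dipstick |
| Follow-up | 28 days after last dose | none | chemistry, HbA1c, urine dipstick |

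The deuterium-glucose samples serve to measure isotope enrichment (Section 4.3.4), so I do not count them as concentrations. Table 10 footnote k describes the Day 35 MMTT samples as deuterium-labelled glucose, whereas the table row and Section 4.3.3 indicate ordinary glucose. I count Day 35 as a glucose day, the reading more favourable to the plan.

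**Step 2. Doses before the first on-treatment value.** The Day 35 baseline sample precedes that day's dose. Doses on Days 1 to 34 come before it: 34 of 35 (34/35 = 97%). Home doses are Days 2 to 7 (6) and Days 9 to 32 (24), so 6 + 24 = 30. Clinic doses are Days 1, 8, 33, 34 and 35, so 5, and 30 + 5 = 35. None of the 30 home-dosing days has a scheduled value. The same count in Part A is 27 of 28 doses before Day 28, but Part A is complete (SAP Section 4).

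**Step 3. Schedule against the Section 3.1.4.3 triggers**

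| Trigger | Needed | Scheduled on treatment |
|---|---|---|
| Capillary readings | for example 3 in one week | 0 |
| Laboratory fasting glucose | at least 2, more than 3 days apart | 1 (Day 35) |

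Scheduled measurements alone can meet neither numeric trigger.

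**Step 4. Symptom lists side by side.** Footnote p names hunger, dizziness, shaking, sweating and irritability, plus feeling unwell in general. Section 3.1.4.3 names thirst, polyuria and blurred vision. The two lists share no symptom.

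**Step 5. What a Day 8 glucose would add.** If it is drawn before that day's dose, the 34 doses split into 7 before Day 8 and 27 from Day 8 to Day 34 (7 + 27 = 34). Days 9 to 34 would still have no scheduled laboratory value.

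**The case against.** The strongest reply is that nothing is contradicted. To monitor need not mean to schedule. Subjects have a meter, adverse events are reviewed at every visit and remote contact, and staff may test on suspicion. Section 3.1.4.3 is a rule for suspected hyperglycaemia, not a screen: reported symptoms open it without any reading, and it sends the investigator to obtain unscheduled laboratory values. Footnote p also covers feeling unwell for any reason. All of this stands. A reader might infer that the plan cannot detect hyperglycaemia, and the documents do not support that. The gap concerns scheduled measurements in subjects without symptoms.

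A second reply is that the risk is modest. Section 1.5 does say "despite the known action of glucagon receptor agonists to increase blood glucose levels", and a reader might take this to mean that MEDI0382 is expected to raise glucose. The same sentence reports significant glucose reductions in treated subjects, and Section 1.4 gives a fall in glucose AUC of 32.8% against 10.2% on placebo. MEDI0382 is also a GLP-1 agonist. Entry requires HbA1c of at most 8.0% and excludes decompensated control. Metformin may be taken from Day 2 to Day 31, and subjects are inpatients from Day 33, so Day 32 is the only day of home dosing that falls in a washout. This reply stands and limits the urgency.

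Third, some text cannot be checked. Sections 4.2.3.1 and 4.3.1.1 are not readable in the public copy and the exploratory endpoints are redacted, so a further glucose check there cannot be ruled out.

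What none of this supplies is a scheduled blood glucose during home dosing, or a reason for footnote p to omit the symptoms on which Section 3.1.4.3 relies.

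**Conclusion.** The point holds for Part B in a limited form. Section 1.6 describes more than the schedule delivers: 34 of 35 doses are given before any scheduled on-treatment plasma or capillary glucose, and no scheduled blood measurement can open the Section 3.1.4.3 rule in a symptom-free subject during home dosing. Detection then depends on symptoms or on staff suspicion. Urine glucose does not feed the rule, and HbA1c is next measured on Day 36, after the last dose.

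It would be tempting to add that few hyperglycaemia events will be reported because glucose was not measured, or that uncontrolled glucose will distort the hepatic glycogen endpoint. The documents give no figures for either, so neither is claimed.

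The conclusion assumes that the tables were read in their correct columns, that Day 35 yields ordinary glucose, and that the unreadable sections add no routine check. This is a safety-monitoring gap that is cheap to narrow, and it does not undermine the primary analysis.

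**What to change.** Reconcile Sections 1.6, 3.1.4.3 and 4.3.3.1 and Table 9 footnote p, for Part B only. Three additions would bring the schedule closer to Section 1.6:

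- Add glucose to the chemistry samples already drawn. Day 8 is the one that adds on-treatment information. Days 1 and 36 give fasted values before the first dose and after the last.
- Add the hyperglycaemia symptoms already named in Section 3.1.4.3 to the meter and diary instruction.
- Ask about those symptoms and about any meter readings at the existing Day 14/15 and Day 21/22 contacts. Under footnote p the diary comes back at the next visit, which after Day 8 is Day 33.

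If nothing is added, reword Section 1.6 to say that monitoring is symptom-driven. Correct Table 10 footnote k if the Day 35 samples are meant for ordinary glucose.

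**Cost.** One analyte, one line in the diary instruction and one in the contact script, with no new visit. SAP Section 3.6.3 already summarises chemistry parameters and their shifts, so no new method is needed. Days 9 to 34 would remain without a scheduled laboratory value. A fasting glucose could also hint at allocation between MEDI0382 and placebo. The protocol should therefore say who sees routine values, while the investigator must still see those needed under Section 3.1.4.3. No dose, threshold or rescue rule is proposed.
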